4.2. Selection of NI dataset

Decision for selection of population for non-inferiority testing

Participants were screened using a local SARS-CoV-2 serology test to ensure that only participants who were seronegative at baseline were enrolled in the main study (or randomized as seropositive

or seronegative at baseline in the sub study). Prior to Primary Analysis, a preliminary blinded evaluation of central N-serology results in main study participants at Day 29 and Day 71 showed that overall, 27% and 38% of participants, respectively, were N-serology positive at these time points. The higher-than-expected N-serology positive status at Day 29 and Day 71 indicated that participants became infected during the study and/or local serology tests were not sufficiently sensitive, affecting the power of the study.

While data following SARS-CoV-2 infections during the study will be excluded from non-inferiority assessments, data from participants who are seropositive at baseline as assessed by central testing could be included in the non-inferiority assessment if serostatus at baseline is considered as an independent variable (scenario 2).

Based on these considerations, only one of two scenarios will be considered for primary analysis. If there is an overall loss of > 40% evaluable data points in the NI set at Day 29 (defined as number of evaluable participants in the NI set at D29/total number of subjects in Table 4), the population in scenario 2 will be used for primary analysis.

Scenario 1 (base case scenario): non-inferiority will be performed on the NI set including participants from the main study and sub-study.

Scenario 2: Non-inferiority analysis will be performed on the PPI set including participants from the main study and sub-study. In this scenario a model accounting for SARS-CoV-2 serostatus at baseline will be used.

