9.4.2. Primary Endpoint(s)

Immunogenicity Endpoints

For each NI comparison between post-dose 1 ($[9 \times 10^{10}$ vp, 2.5×10^{10} , 7×10^{10} vp, 3.5×10^{10} vp, or 1.25×10^{10} vp] versus 5×10^{10} vp), estimated humoral immune response differences will be expressed as ratios of GMCs of S-ELISA (GMC [9×10^{10} vp, 2.5×10^{10} , 7×10^{10} vp, 3.5×10^{10} vp, or 1.25×10^{10} vp]/GMC 5×10^{10} vp), 28 days post-dose 1 with corresponding 97.5% confidence interval (CI) (2-sided) (Type 1 error 0.0125 for each comparison).

Similarly, for each NI comparison between post-dose 2 ($[9 \times 10^{10}$ vp, 2.5×10^{10} , 7×10^{10} vp, 3.5×10^{10} vp, or 1.25×10^{10} vp] versus 1- or 2-doses of 5×10^{10} vp), estimated humoral immune response differences will be expressed as ratios of GMCs of S-ELISA (GMC [9×10^{10} vp, 2.5×10^{10} , 7×10^{10} vp, 3.5×10^{10} vp, or 1.25×10^{10} vp]/GMC 5×10^{10} vp), 28 days post-dose 1 or 14 days post-dose 2 with corresponding 97.5% confidence interval (CI) (2-sided) (Type 1 error 0.0125 for each comparison).

In both sets (1 dose and 2 doses) of comparisons above, 97.5% CIs (2-sided) for mean difference in log₁₀-transformed S-ELISA titers between 2 groups will first be calculated and then back-transformed to the original scale to obtain the GMC ratios and the associated 97.5% CIs (2-sided). Non-inferiority between the groups will be established if the 97.5% CI of the estimated GMC ratio of the groups entirely lies above 2/3.

In the 1-dose (dose 1 of the 2-dose regimen) and 2-dose set NI comparisons, hierarchical testing after administration of a single-dose and 2 doses will be applied independently, as reflected in the Decision Tree-based Hypothesis Testing (Figure 2 and Section 9.1). The non-inferiority analyses will be done on the NI analysis set.

- Note: If a large number of participants become infected during the study (as assessed eg, by N-seroconversion or by PCR confirmation) or are SARS-CoV-2 seropositive at baseline, the main study and sub-study participants (seronegative at baseline) may be combined.
- If the power of the combined main study and sub-study is less than 80% then seropositive subjects at baseline will be included in the analysis. Further details of the analysis will be provided in the SAP.

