3. SAMPLE SIZE DETERMINATION

The number of participants chosen is to provide sufficient power for the non-inferiority comparisons.

The following assumptions were made in the sample size determinations:

Log transformed (\log_{10} scale) immune response data are normally distributed

A common standard deviation (SD): SD=0.5 (\log_{10} scale) of the immune response log transformed data

Non-inferiority margin = $\log_{10}(2/3) = -0.176$

Alpha = 0.0125 (1-sided) for 1- and 2-dose NI comparisons

- Alpha = 0.025 (one-sided). Using a Bonferroni correction, Type I error will be split equally over the 1-dose and 2-dose comparisons: 0.0125 (1-sided) for 1- and 2-dose NI comparisons

Power = 90%

Based on the above assumptions, and approximately a 10% dropout, a sample size of 225 participants per active vaccine group (see [Table 2](#)) is needed to detect non-inferiority of testing 1-dose and 2-doses of 9×10^{10} vp, 2.5×10^{10} vp, 7×10^{10} vp, 3.5×10^{10} vp, and 1.25×10^{10} vp Ad26.COV2.S as the test groups versus 1-dose and 2-doses of 5×10^{10} vp Ad26.COV2.S (release titer) as the reference groups, with 90% power (main study sample size assessment).

The originally intended NI population was comprised of participants from the main study who were SARS-CoV-2 seronegative at baseline and non-previously vaccinated. In addition, participants becoming infected with SARS-CoV-2 during the study are excluded from this population from the time of infection.

Participants were screened using a local SARS-CoV-2 serology test to ensure only participants who were seronegative at baseline were enrolled in the main study. However, a preliminary blinded evaluation of central N-serology results in main study participants at Day 29 and Day 71 showed that overall, 27% and 38% of participants, respectively, were N-serology positive at these time points. The higher-than-expected N-serology positive status at Day 29 and Day 71 indicated that participants became infected during the study and/or local serology tests were not sufficiently sensitive, affecting the power of the study.

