5.5.3.1. Non-Inferiority Analysis- Immune Response

Formal NI testing will be applied to demonstrate non-inferiority of immunogenicity. Non-inferiority will be analyzed by vaccine dose levels. As described in section 4, only one of the two scenarios will be considered for non-inferiority hypothesis testing at primary analysis. If there is an overall loss of $> 40\%$ evaluable data points in the NI set at Day 29 (defined as number of evaluable participants in the NI set at D29/total number of subjects in Table 4), the population in scenario 2 will be used for primary analysis.

- **Scenario 1 (base case scenario):** non-inferiority will be performed on the NI set including participants from the main and the sub study. A linear regression analysis with only one main effect (dose level) will be fitted, with log-transformed (\log_{10} scale) SARS-CoV-2 S-protein specific antibody concentration (S-ELISA) as the response variable and dose level as the independent variable.
- **Scenario 2:** Non-inferiority will be performed on the PPI set including participants from the main study and sub-study. A linear regression analysis with two main effects (dose level and SARS-CoV-2 serostatus at baseline) will be fitted, with log-transformed (\log_{10} scale) SARS-CoV-2 S-protein specific antibody concentration (S-ELISA) as the response variable and dose level and SARS-CoV-2 serostatus at baseline as the independent variables.

Participants with missing serostatus at baseline will not be included in this analysis.

Level of Significance

For each of the 1-dose and 2-dose vaccine regimens hypothesis, the type I error rate α will be set to 0.0125 (1-sided) and non-inferiority (NI) tests will be confirmed by constructing the corresponding 97.5% confidence interval (2-sided) which is equivalent to using $\alpha = 0.025$ (1-sided) with 98.75 (1-sided CI).

Multiplicity Adjustment

The family-wise error rate (FWER) at $\alpha = 0.025$ (one-sided), will be controlled by:

Splitting the Type I error rate $\alpha = 0.025$ into two (i.e., $\alpha = 0.0125$) using Bonferroni correction for the independently tested 1 and 2 doses NI hypotheses (see

[Figure 1](#)).

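### The analysis population for both non-inferiority families is chosen from Day 29 loss alone, so the 2-dose v 2-dose tests at Day 71 can stay in the NI set with power below the protocol's 80% criterion

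*SAP*

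**What the plan says.** SAP 4.2 and 5.5.3.1 define two populations for the formal tests. Scenario 1 uses the NI set (PPI participants centrally seronegative at baseline). Scenario 2 uses the PPI set with baseline serostatus in the model. Both pool main study and sub-study. Scenario 2 applies "If there is an overall loss of > 40% evaluable data points in the NI set at Day 29", counted against the Table 4 total. SAP 5.5.3.1 adds that "only one of the two scenarios will be considered for non-inferiority hypothesis testing at primary analysis". There is no Day 71 condition and no separate choice for the 2-dose family.

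SAP 3 and 4.2 report a blinded look at central N-serology in the main study at Days 29 and 71, which "showed that overall, 27% and 38% of participants, respectively, were N-serology positive at these time points". Under SAP 4.1, samples from the first post-baseline N-positive result onward leave the PPI set, and so the NI set.

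Protocol 9.4.2 states a different criterion: "If the power of the combined main study and sub-study is less than 80% then seropositive subjects at baseline will be included in the analysis". It names no time point or comparison and leaves further detail to the SAP.

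**The concern.** There are two primary families. The 1-dose family (five tests) is measured at Day 29. In the 2-dose family (ten tests) the test arm is measured 14 days after dose 2, at Day 71. Loss from infection accumulates between the two visits, and so do missed or out-of-window second doses and off-study vaccination. A count taken at Day 29 therefore understates the loss that the 2-dose family will face.

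The rule can then keep Scenario 1 on acceptable Day 29 numbers while the Day 71 tests run at power for which protocol 9.4.2 would bring in baseline seropositives. Testing within the family is sequential. If the tree follows the listed order, a miss on an early test such as 2a2 or 2b2 also stops the later ones.

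**Working it through.** **Inputs**
- One-sided alpha 0.0125 per family (SAP 3: "Type I error will be split equally over the 1-dose and 2-dose comparisons: 0.0125 (1-sided) for 1- and 2-dose NI comparisons"), SD 0.5 on the log10 scale and margin log10(2/3) = −0.176 (SAP 3).
- Group sizes from SAP Table 4: 265 for the 9, 5, 2.5 and 1.25×10^10 groups; 225 for the 7 and 3.5×10^10 groups; total 4×265 + 2×225 = 1510.
- N-positive: 27% at Day 29 and 38% at Day 71. These are main-study figures, assumed to hold for the sub-study seronegatives.
- Assumptions not in the documents: true GMC ratio 1, and other loss *o* independent of N-status. *o* is varied; the protocol's design dropout of 10.2% is the reference case.
- The bracketed definition in SAP 4.2 (evaluable/total) is retention, so loss is taken as 1 minus that ratio.

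**Reproducing the plan.** Noncentral-t power for two equal arms of n(1 − loss), at 10 to 60% loss:
- 265 v 265: 94.5, 91.5, 87.3, 81.2, 73.0, 62.1% (Table 4: 94, 91, 87, 81, 73, 62).
- 225 v 225: 90.2, 86.2, 80.8, 73.8, 65.0, 54.2% (Table 4: 90, 86, 81, 74, 65, 54).

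All 12 cells agree within 1 point. The real comparison for the 225 groups is 225 v 265, used below.

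**Loss at each visit.** Loss = 1 − (1 − N-positive)(1 − *o*). At *o* = 10.2%:
- Day 29: 1 − 0.73×0.898 = 34.4%. Scenario 1 is kept.
- Day 71: 1 − 0.62×0.898 = 44.3%. This is above 40%, but the rule does not look there.

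**Power in the 2-dose family at *o* = 10.2%.** Evaluable numbers are 265×0.62×0.898 = 148 and 225×0.62×0.898 = 125 at Day 71, and 265×0.73×0.898 = 174 for the reference at Day 29.

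| Comparison | 265 group | 225 group |
|---|---|---|
| 2-dose v 2-dose (2a2 to 2e2) | 78% | 74% |
| 2-dose v 1-dose (2a1 to 2e1) | 81% | 77% |

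**Range of other loss for which this happens**
- Scenario 1 is kept while 0.73(1 − *o*) ≥ 0.60, so *o* ≤ 1 − 0.60/0.73 = 17.8%.
- 265 v 265 drops below 80% at 41.7% loss, so *o* > 1 − 0.583/0.62 = 6.0%.
- 225 v 265 drops below 80% at 36.5% loss, so at Day 71 it is already at 79% with *o* = 0.
- All five 2-dose v 2-dose tests are therefore below 80%, with Scenario 1 kept, for *o* from about 6% to 17.8%. At the upper end, Day 71 loss is 49% and power is 74% and 70%.

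**If enrolment was that of protocol Table 7** (252 and 212 per arm; total 4×252 + 2×212 = 1432) and the denominator stays 1510:
- Scenario 1 is kept up to *o* = 1 − 906/(1432×0.73) = 13.3%, where 906 = 0.60×1510.
- At *o* = 10.2%, Day 29 loss is 37.8% (Scenario 1) and 2-dose v 2-dose power is 76% (252 v 252) and 71% (212 v 252).

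**What Scenario 2 recovers at Day 71.** If a share *b* is centrally seropositive at baseline, retention is (0.62 + *b*)×0.898, with SD 0.5 assumed to hold after adjustment. The documents do not give *b*.

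| *b* | 265 v 265 | 225 v 265 |
|---|---|---|
| 0 | 78% | 74% |
| 5% | 81% | 78% |
| 10% | 84% | 81% |

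**The case against.** The strongest reply is that switching population does not undo the loss in question. SAP 4.2 excludes data after in-study infection from the non-inferiority assessment under either scenario. So far as the rise from 27% to 38% is new infection, a Day 71 trigger recovers none of it; only baseline seropositives come back. This stands and limits the benefit. It does not justify ignoring Day 71, because the protocol's remedy is that same inclusion of baseline seropositives.

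Three other points narrow the claim:
- A reader might infer that all ten 2-dose tests fall below 80%. They need not: 2a1 to 2e1 use the Day 29 reference, and at 10.2% other loss 2a1, 2b1 and 2e1 stay at about 81%.
- A reader might take Scenario 1 at Day 29 to be the likely outcome. The documents do not establish that. The NI set also loses participants who are S-positive only, or whose baseline serostatus is missing, and the fixed Table 4 denominator raises the computed loss if enrolment fell short.
- The shortfall in the 7 and 3.5×10^10 groups is partly a matter of the 40% cut itself. Table 4 gives 74% for those groups at 40% loss at any visit.

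It is also fair that one population for both families is simpler, that the trigger is a prespecified pooled count, and that SAP 5.5.3 permits descriptive non-inferiority on the PPI set. That analysis is optional and cannot replace the formal test. Protocol 9.4.2 does delegate detail to the SAP, but a rule that never looks at Day 71 can leave its stated criterion unmet.

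**Conclusion.** The mismatch is real and should be corrected. A Day 29 count decides the population for tests measured at Day 71, and the SAP's own figures show the two visits differ by 11 points in N-positivity. With other loss of about 6% to 17.8% (up to about 13.3% on protocol Table 7 enrolment), Scenario 1 is kept while all five 2-dose v 2-dose tests are below 80% power. The shortfall is moderate: 2 points for the 265 groups and 6 for the 225 groups at 10.2% other loss.

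This rests on main-study N-positivity applying throughout, SD 0.5, a true ratio of 1 and an assumed other loss. The consequence is reduced power; no bias or type I error inflation follows. Nor do the documents support the inference that a Day 71 trigger would guarantee 80%, since the baseline-seropositive share is not given.

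**What to change.** Before unblinding, amend SAP 4.2 and 5.5.3.1 so that:
- the choice for the 2-dose family also uses pooled blinded evaluable counts at Day 71;
- the criterion is the protocol's, namely power below 80% for the comparisons concerned, with the calculation stated;
- the non-chosen scenario is reported alongside;
- the text says that Scenario 2 recovers only participants centrally seropositive at baseline, not in-study infections, and may not reach 80%.

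The cost is SAP wording and a count of data already collected. The drawback is that a trigger split by family may put the two families on different populations, including for the shared Day 29 reference group, and this must be labelled. Applying the worse of the two time points to both families avoids it.

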Per amendment 5, an additional enrollment of adult participants 18 to 55 years, inclusive, will enroll into the sub study, into group 1, 3, 5 and 6 to further characterize the innate, pro-inflammatory and other relevant (e.g., pro-thrombotic) response to the Ad26.COV2.S to better understand a possible risk to TTS events. Participants will receive Ad26.COV2.S administered IM.

A target of approximately 240 participants (approximately 40 seronegative and approximately 20 seropositive participants per dose regimen) will be enrolled in the sub study and will receive a 2-dose vaccination regimen at either 9×10^{10} vp, 5×10^{10} vp, 2.5×10^{10} vp or 1.25×10^{10} vp.

Table 3 : Schematic Overview of Study Design and Groups for the Sub Study

Group	N seronegative	N seropositive	Day 1 Vaccination 1	Day 57 Vaccination 2
1	N ~ 40	N ~ 20	Ad26.COV2.S 9×10^{10} vp	Ad26.COV2.S 9×10^{10} vp
3	N ~ 40	N ~ 20	Ad26.COV2.S 5×10^{10} vp	Ad26.COV2.S 5×10^{10} vp
5	N ~ 40	N ~ 20	Ad26.COV2.S 2.5×10^{10} vp	Ad26.COV2.S 2.5×10^{10} vp
6	N ~ 40	N ~ 20	Ad26.COV2.S 1.25×10^{10} vp	Ad26.COV2.S 1.25×10^{10} vp

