For the sub-study (initiated to further characterize the innate, pro-inflammatory and other relevant (e.g., prothrombotic) responses to Ad26.COV2.S to better understand a possible risk to TTS events), a target of approximately 240 participants will be enrolled and will receive a 2-dose vaccination regimen at either 9×10^{10} vp, 2.5×10^{10} vp, 5×10^{10} vp, or 1.25×10^{10} vp. As participants in the sub-study share common blood sampling timepoints with the main study, data from both cohorts can be merged for analyses. Due to the higher-than-expected N serology positive results in the main study affecting the power of the study, the non-inferiority assessment will combine participants from the main study and sub-study.

Table 4 below shows how, when combining main and sub study participants (randomized as SARS-CoV-2 seronegative at baseline based on local serology by finger prick testing), the power is affected due to a hypothetical 10%, 20%, 30%, 40%, 50% and 60% loss of evaluable participants (lost due to various reasons, e.g. lost to follow-up, participants with major protocol deviations with impact on immunogenicity, participants who become infected with SARS-CoV-2, participants who received their vaccination outside the allowed window, etc.).

Table 4: Impact of loss of evaluable subjects on NI assessment power

Dose level	Sample size at enrollment per arm (main study + sub study)	Group	% loss of evaluable participants since enrollment					
			10%	20%	30%	40%	50%	60%
9x1010 vp	265(225+40)	1	94%	91%	87%	81%	73%	62%
2.5x1010 vp	265(225+40)	5	94%	91%	87%	81%	73%	62%
7x1010 vp	225 (225+0)	2	90%	86	81%	74%	65%	54%
5x1010 vp	265(225+40)	3	94%	91%	87%	81%	73%	62%
3.5x1010 vp	225 (225+0)	4	90%	86	81%	74%	65%	54%
1.25x1010 vp	265(225+40)	6	94%	91%	87%	81%	73%	62%

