4. POPULATIONS (ANALYSIS SETS) FOR ANALYSIS

For vaccine studies, study intervention assignment will follow the as treated principle: all analyses (including safety, immunogenicity) will be analyzed by the received vaccine.

Analysis Sets	Description
All screened participants (ALL)	The “all screened participants” set includes all participants that were screened, regardless of whether they were enrolled and/or randomized.
All randomized participants (ALL RANDOMIZED)	The “all randomized participants” set includes all participants that were randomized to one of the treatment groups.
Full Analyses Set (FAS)	The Full Analysis Set will include all participants with at least one vaccine administration documented
Per Protocol Immunogenicity Set (PPI)	The Per Protocol Immunogenicity population will include all randomized and vaccinated participants for whom immunogenicity data are available excluding participants with major protocol deviations expected to impact the immunogenicity outcomes (see section 4.1). In addition, samples obtained after missed vaccinations or samples obtained from participants after SARS-CoV-2 infection occurring after screening (if applicable) will be excluded from the analysis set (see below section 4.1).
NI Analysis Set	The NI analysis set will include all PPI participants who are SARS-CoV-2 seronegative at study entry ^a .

^a SARS-CoV-2 seronegative as assessed by central testing (based on S- and/or N- serology at baseline)

NB. As detailed in Section 4, formal non-inferiority hypothesis testing will be performed on either the NI set or on the PPI set under different scenarios (Scenario 1 or Scenario 2, respectively).

Further details on the selection of PPI and NI set are described below.

The safety and reactogenicity analyses will be censored at the date of unblinding or the receipt of an unscheduled vaccine, whichever event occurs first. AEs reported after unblinding or receipt of an unscheduled vaccine, whichever comes first, will be listed.

The immunogenicity analyses will be censored at the date of the receipt of an unscheduled vaccine. Immunogenicity samples taken after the receipt of an unscheduled vaccine will be included in the listings and flagged.

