5.5.3. Analysis Methods

Formal non-inferiority hypothesis testing will be performed on either the NI set (Scenario 1) or on the PPI set (Scenario 2) as described in Section 4.

Descriptive non-inferiority and additional immunogenicity assessments may be performed on other populations and subgroups (e.g., PPI, or on participants in the PPI who are SARS-CoV-2 seropositive at baseline, etc.).

Immunogenicity analyses may also be done on the FAS (participants who became infected during the study will be analyzed as a subgroup and will be shown in the graphs using different colors

and symbols). Samples taken outside of the allowed windows as described in section 5.1.3 (included in the FAS analysis and excluded from the output in the analysis on PPI) will be included and flagged in the listings as results not included in the PPI analyses.

Key immunogenicity subgroup analyses will also be performed by age group, sex, BMI, race, ethnicity, and serostatus at baseline, as defined in Section 5.1.5.

Categorical variables will be summarized with a frequency table showing counts and percentages.

Continuous variables will be summarized using the following statistics, as appropriate: number of observations, geometric mean, arithmetic mean (mean), 95% confidence interval (CI) for the mean, standard deviation (SD), standard error (SE), median, quartiles (Q1 and Q3), minimum and maximum.

Data listings, participant profiles and/or participant narratives may be provided as appropriate.

Binary variables will be summarized using the following statistics: number of observations, percentages, and Exact Clopper-Pearson 95% CIs.

Formal NI testing will be applied to demonstrate NI of 1-dose and 2-doses of 9×10^{10} vp, 7×10^{10} vp, 3.5×10^{10} vp, 2.5×10^{10} vp and 1.25×10^{10} vp Ad26.COV2.S versus 1-dose and 2-doses of 5×10^{10} vp Ad26.COV2.S (release titer), using a NI margin of 2/3 for the GMC ratios.

The following 2 sets of hypotheses (1 dose and 2 doses) will independently be tested sequentially:

Post-dose 1

1a) NI after 1-dose of Ad26.COV2.S 9×10^{10} vp versus 1-dose of Ad26.COV2.S 5×10^{10} vp (release titer)

1b) NI after 1-dose of Ad26.COV2.S 2.5×10^{10} vp versus 1-dose of Ad26.COV2.S 5×10^{10} vp (release titer)

1c) NI after 1-dose of Ad26.COV2.S 7×10^{10} vp versus 1-dose of Ad26.COV2.S 5×10^{10} vp (release titer)

1d) NI after 1-dose of Ad26.COV2.S 3.5×10^{10} vp versus 1-dose of Ad26.COV2.S 5×10^{10} vp (release titer)

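### The rule that picks the primary non-inferiority population triggers on loss above 40% but defines loss as the fraction retained (SAP 4.2 and 5.5.3.1)

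*SAP*

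**What the plan says.** SAP 4.2 allows only one of two scenarios to be the primary analysis.

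- Scenario 1 is the default: "Scenario 1 (base case scenario): non-inferiority will be performed on the NI set", with dose level as the only model term (SAP 5.5.3.1).
- Scenario 2 uses the PPI set, with dose level and baseline SARS-CoV-2 serostatus in the model.

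The switch to Scenario 2 is worded "If there is an overall loss of > 40% evaluable data points in the NI set at Day 29". The bracket that follows explains the quantity as "defined as number of evaluable participants in the NI set at D29/total number of subjects in Table 4". SAP 5.5.3.1 repeats the trigger and the bracket. No other section corrects either.

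Three other places show which direction was meant. Scenario 1 is labelled the base case. The columns of SAP Table 4 are headed as percentage "loss of evaluable participants since enrollment". Protocol 9.4.2 says: "If the power of the combined main study and sub-study is less than 80% then seropositive subjects at baseline will be included".

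**The concern.** Evaluable divided by total is the proportion kept. If the bracket is programmed as it stands, the plan leaves its base case when few data are lost and returns to it only when 60% or more are lost, which reverses the purpose of the rule.

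The rule determines the analysis set and the regression model for all 15 primary non-inferiority tests: five after one dose (1a to 1e) and ten after two doses (2a1 to 2e2). Selecting Scenario 2 by mistake would bring baseline-seropositive participants into the primary analysis. Some are planned: the sub-study enrols "approximately 40 seronegative and approximately 20 seropositive participants per dose regimen" in Groups 1, 3, 5 and 6, so about 4 × 20 = 80 in those groups and none in Groups 2 and 4. The rest are main-study participants who passed local screening but were positive centrally, since the NI set requires participants to be "SARS-CoV-2 seronegative as assessed by central testing (based on S- and/or N- serology at baseline"). Their number is not given.

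**Working it through.** **Reproducing Table 4, to which the trigger refers.** Inputs from SAP 3: SD 0.5 on the log10 scale, margin 0.1761, one-sided alpha 0.0125 (z = 2.2414). A true difference of 0 is assumed; the SAP does not state it. With n evaluable per arm in both arms, power = Φ(0.1761 / (0.5·√(2/n)) − 2.2414).

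| Loss | 265 per arm: computed (stated) | 225 per arm: computed (stated) |
|---|---|---|
| 10% | 94.6% (94%) | 90.4% (90%) |
| 40% | 81.6% (81%) | 74.3% (74%) |
| 60% | 62.6% (62%) | 54.8% (54%) |

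Table 4 reproduces, so the fault is confined to the bracket. Read as loss, 40% corresponds to 81% power for the 265-per-arm groups. That sits next to the 80% criterion in Protocol 9.4.2 and supports the intended direction.

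**Denominator.** Table 4 total = 4 × 265 + 2 × 225 = 1510.

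**The two rules, with E evaluable in the NI set at Day 29.**

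- As written: Scenario 2 if E/1510 > 0.40, so E > 604.
- As intended: Scenario 2 if 1 − E/1510 > 0.40, so E < 906.

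| E | True loss | As written | As intended |
|---|---|---|---|
| 906 to 1510 | 40% or less | Scenario 2 | Scenario 1 |
| 605 to 905 | between 40% and 60% | Scenario 2 | Scenario 2 |
| 0 to 604 | 60% or more | Scenario 1 | Scenario 2 |

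The rules agree only in the middle band, always on Scenario 2. As written, baseline seropositives would be brought in at 10% loss, where Table 4 gives 94% power (265 per arm). They would be left out at 60% loss or more, where it gives at most 62% (265 per arm) or 54% (225 per arm).

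**Illustration.** SAP 3 and 4.2 report 27% central N-positivity at Day 29 in the main study. This is not the NI-set loss: baseline S-positives, missing serostatus, deviations and out-of-window samples add to it. Assume that 27% also holds in the sub-study and that other loss is between 0 and 10.2% (the protocol's planned dropout). Then E = enrolled × 0.73 × (1 − other loss). Two enrolment totals are used: 1510, and the 4 × 252 + 2 × 212 = 1432 implied by Protocol Table 7. Both are divided by the SAP's 1510.

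| Enrolled | Other loss | E | E/1510 | Loss | As written | As intended |
|---|---|---|---|---|---|---|
| 1510 | 0% | 1102 | 0.73 | 27.0% | Scenario 2 | Scenario 1 |
| 1510 | 10.2% | 990 | 0.66 | 34.4% | Scenario 2 | Scenario 1 |
| 1432 | 0% | 1045 | 0.69 | 30.8% | Scenario 2 | Scenario 1 |
| 1432 | 10.2% | 939 | 0.62 | 37.8% | Scenario 2 | Scenario 1 |

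The conflict ends once other loss exceeds 1 − 906/(0.73 × 1510) = 17.8%, or 1 − 906/(0.73 × 1432) = 13.3%.

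**The case against.** The strongest reply is that nobody would be misled. The operative word is loss, Table 4 is indexed by loss, Scenario 1 is the base case, and the 80% power criterion points the same way. The bracket can even be read as giving only the numerator and denominator of the evaluable proportion, with loss understood as its complement. The intent is indeed clear, which is why this is a drafting error and not an open question of design. The text does not state that charitable reading, however, and a rule that selects the primary analysis should be executable as written.

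It can also be said that no effect on this trial is shown. The actual Day 29 loss is unknown, the allowance for other loss is borrowed from planned dropout, and a loss between 40% and 60% cannot be excluded. All of that stands. Nor has any bias, type I error inflation or power change from a wrong choice been calculated; Scenario 2 is itself prespecified and adjusts for serostatus.

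On blinding, the trigger is a pooled count that needs no treatment codes, and SAP 4.2 introduces it after a blinded review of serology. Silence on when the count is made is therefore a missing detail, not an error. A sentence would still help: SAP 5.1.3 limits changes to the analysis windows to the time before unblinding, no such limit is set for this choice, and SAP 5.1.1 and 7 provide for an unblinded sponsor.

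**Conclusion.** The concern holds. Both statements of the rule define loss as its complement. Followed literally, the rule selects the opposite scenario whenever true loss is 40% or less (906 or more of 1510 evaluable) or 60% or more (604 or fewer). These cut-points rest only on the Table 4 sample sizes. Whether the error would change the primary analysis depends on a Day 29 loss that the documents do not give. Under the stated assumptions of 27% N-positivity throughout and up to 10.2% other loss, the readings conflict; with other loss above 13.3% to 17.8%, and total loss still below 60%, they do not. It should be corrected because it governs all 15 primary tests, although the intention is not in doubt.

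**What to change.** In SAP 4.2 and 5.5.3.1, replace the bracket with: loss = 1 − (NI-set participants evaluable at Day 29 ÷ Table 4 total). Writing the total as 1510 would also remove doubt about the denominator, because Protocol Table 7 implies 1432. It is advisable, though secondary, to add that the count is made on blinded data before unblinding. The 40% threshold, the Day 29 visit and the two scenarios do not change. The cost is one line of wording in two places, with no new data and no change to the design.
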